4. STATISTICAL ANALYSES

4.1. General Considerations

All analyses will use SAS version 9.4 or higher. The schedule of study assessments and time points are provided in the current PREVAIL master protocol and STRIVE sub-study.

Data will be provided in by-participant listings for the All Enrolled Set, unless otherwise specified.

Efficacy endpoints will be summarized by TDF/TD discontinued (participants who discontinued TDF/TD when the TDF/TD discontinuation criteria were met in the Follow-up period) and overall for each cohort.

Continuous variables will be summarized using the following descriptive summary statistics: the number of participants (n), mean, standard deviation (SD), median, Q1 (first quartile), Q3 (third quartile), minimum value (min), and maximum value (max), unless otherwise specified. In general, the precision of the measurement for each continuous variable will be used to determine the number of decimal places to present in tables, figures, and derived listings. Minimum and maximum values will be reported with the same precision as the units of measure. The mean and median will be reported to 1 additional decimal place, and the SD will be reported to 2 additional decimal places. Any values that require transformation to standard units (metric or SI) will be converted with the appropriate corresponding precision.

Categorical variables will be summarized using counts and percentages. Percentages will be rounded to one decimal place, except 100% will be displayed without any decimal places, and percentages will not be displayed for zero counts.

Baseline value: Unless otherwise specified, the baseline value will be defined as the most recent non-missing (scheduled or unscheduled) measurement collected prior to the initial administration of study intervention. If baseline cannot be determined due to missing data, no derivation will be performed, and baseline will be set to missing.

Change (absolute change) from baseline will be calculated as post-baseline value – baseline value.

Study day: The study day of an event/measurement is defined as the relative day of the event/measurement starting with the date of the first study drug administration (reference date) as Day 1 (there will be no Day 0).

The study day of event/measurement occurring before the first study drug administration will be calculated as:

$$\text{Study Day} = (\text{Date of event/measurement} - \text{Date of first study drug administration})$$

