- For efficacy response variables, the missing equals failure (MEF) approach will be used for the analysis, except for the sensitivity analysis for the primary endpoint described in [Section Error! Reference source not found.](#). The sensitivity analysis will be conducted to evaluate the impact of missing data, in which missing data will be imputed.
- Missing data will not be imputed, and will be considered as missing data that will not be included in the data summary statistics and analysis. Qualitative data will be imputed as follows:
 1. HBV DNA, for the analysis of the primary endpoint:

- a. If the missing data is reported as “Target Not Detected (TND)”, then the missing data point will be imputed as 0.
- b. If the missing data is reported as “< LLOQ”, then the missing data point will be imputed 1 unit less than the LLOQ value. That’s the LLOQ for HBV DNA is 20 IU/mL, so 19 IU/mL will be imputed.

2. HBs(e)Ag and Anti-HBs(e), for the analyses of primary and secondary efficacy endpoints:
If the missing data is reported as “Not Detected” or “Nonactive”, then the missing data point will be imputed as 0.
3. HBV RNA, for the analysis of an exploratory endpoint:
 - a. If the missing data is reported as “Not Detected”, then the missing data point will be imputed as 0.
 - b. If the missing data is reported as “< LLOQ”, then the missing data point will be imputed 1 unit less than the LLOQ value. That’s the LLOQ for HBV RNA is 0.49 log U/mL, so 0.48 log U/mL will be imputed.
 - c. If the missing data is reported as “> upper limit of quantification (ULOQ)”, then the missing data point will be imputed as 1 unit greater than the value of ULOQ. E.g., The ULOQ for HBV RNA is 6.0 log U/mL, so 6.1 log U/mL will be imputed.
 - d. If the missing data is reported as “Invalid” or “Quantity Not Sufficient (QNS)”, then the missing data will not be imputed and considered as missing data.
4. HBcrAg, for the analysis of an exploratory endpoint:
 - a. If the missing data is reported as “TND”, then the missing data point will be imputed as 0.
 - b. If the missing data is reported as “Target Detected (TD)”, then the missing data point will be imputed as 1 unit less than the LLOQ. That’s the LLOQ is $3.0 \log_{10} \text{U/mL}$, so $2.9 \log_{10} \text{U/mL}$ will be imputed.

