
9. Proportion of participants achieving sustained suppression of HBV DNA (< LLOQ) with HBsAg loss (< 0.05 IU/mL) after discontinuation of all treatment:
 
a. at 24 weeks
 
b. at the F48 Follow-Up visit
 
11. Proportion of participants achieving sustained suppression of HBV DNA (< LLOQ) after discontinuation of all treatment:
 
a. at 24 weeks
 
b. at the F48 Follow-Up visit
	
Due to early study termination, modification to timepoints of a. and b. as below:
 
a) at 24 weeks after discontinuation of all treatments (an analysis window of 168 ± 14 days will be applied to capture data around the 24 weeks timepoint, following the rules in Appendix 2 for data selection)
 
b) at the last Follow-Up visit, for participants who have > 24 weeks of discontinuation, after discontinuation of all treatments
 
c) at the last Follow-Up visit after discontinuation of all treatments (all participants will be included in the denominator)
 
Specifically, for a) and b), the denominator used in the percentage calculation will exclude participants with uncertain NRTI discontinuation status due to early study termination (e.g., no Follow-Up 12 visit).
 
The number and percentage of participants achieving
 
 • sustained suppression of HBV DNA (< LLOQ) • sustained suppression of HBV DNA (< LLOQ) with HBsAg loss (< 0.05 IU/mL) 
will be summarized by cohort with the two-sided 95% Clopper-Pearson CI.
 
In addition, the number and percentage of participants achieving
 
 • sustained suppression of HBV DNA (< LLOQ), allowing transient viremia

	
 • sustained suppression of HBV DNA (< LLOQ) with HBsAg loss (< 0.05 IU/mL), allowing transient viremia where transient viremia is defined as HBV DNA \geq LLOQ or HBsAg \geq LLOQ for \leq 35 days, adapted from the 2022 American Association for the Study of Liver Diseases (AASLD) – The European Association for the Study of the Liver (EASL) functional cure definition (AASLD-EASL, 2022), will be analyzed similarly. 
Similarly, the analyses above will be repeated after replacing “HBsAg loss (<0.05 IU/mL) with “HBsAg < 100 IU/mL”. Accordingly, the transient viremia is defined as HBV DNA \geq LLOQ or HBsAg \geq 100 IU/mL for \leq 35 days, adapted from the 2022 AASLD-EASL partial functional cure definition (AASLD-EASL, 2022).

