4.5. Exploratory Endpoints Analysis

4.5.1. Exploratory Efficacy Analysis

The analyses of the following exploratory efficacy endpoints will be conducted based on the FAS, unless otherwise specified. The numbering in the table below is consistent with the numbering of the endpoints in [Table 1](#). HBV RNA and HBcrAg values will be provided in a by-participant listing.

[figure not shown]
Exploratory Endpoints	Analysis Methods
1. Additional viral parameters associated with HBV and/or study intervention(s), including but not limited to HBV RNA and HBcrAg	
The observed values and the absolute change from baseline values at each visit up to End of Follow-up will be summarized using descriptive statistics (n, mean, SD, median, Q1, Q3, min, max) by cohort for the following HBV viral parameters:
 
 • HBV RNA in \log_{10} U/mL • HBcrAg in \log_{10} U/mL

Exploratory Endpoints	Analysis Methods
2. CCI	CCI
3. CCI	CCI
4. Emergence of viral resistance to study intervention(s)	Not covered by this SAP, will be analyzed separately.
7. For HBeAg-positive participants: time to achieve HBeAg loss (undetectable HBeAg) and/or anti-HBe seroconversion	Time to HBeAg loss and/or anti-HBe seroconversion will be summarized as a continuous variable. Participants with HBeAg loss with or without anti-HBe seroconversion will be listed.
8. Proportion of participants meeting criteria for NRTI discontinuation or retreatment in the study	The number and percentage of participants who meet NRTI discontinuation criteria NRTI retreatment criteria will be summarized by cohort. A by-participant listing will be provided for participants who met NRTI discontinuation criteria and retreatment criteria.
9. HBV DNA levels and change from baseline across timepoints in the study 10. Nadir and maximum change of HBV DNA level from baseline in the study	The observed values and the absolute change from baseline values of HBV DNA in both log IU/mL and IU/mL: a. at each visit b. at nadir up to EOS, will be summarized using descriptive statistics (n, mean, SD, median, Q1, Q3, min, max) by cohort. In addition, the change from baseline in \log_{10} IU/mL and absolute value in \log_{10} IU/mL at

Exploratory Endpoints	Analysis Methods
	each visit will be plotted for each participant by cohort.

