14. Proportion of participants with virological relapse (defined as either (1) an increase of $\geq 1 \log_{10}$ HBV DNA IU/mL above nadir for at least 2 consecutive visits OR (2) quantifiable HBV DNA of $\geq 1 \log_{10}$ IU/mL above LLOQ for at least 2 consecutive visits after being < LLOQ)	The number and percentage of participants with virological relapse will be summarized during the study.

CCI

CCI

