Section 9.4.1: TEAE definition for this sub-protocol: An AE that is reported with an onset date on or after the start of study intervention(s) until end of Follow-Up Period.	TEAE is defined as any AEs reported with an onset date on or after the first dose of study intervention(s) until the end of TE Period. The TE Period is defined as the time period on or from the start of study intervention(s) until the last dose of VIR-2218 + 30 days, or VIR-3434 + 24 weeks, or PEG-IFN α + 30 days, or TDF/TD + 30 days, whichever is later.
Protocol Section 9.5: Three interim analyses will be conducted for each cohort to evaluate the efficacy endpoints at Week 24, EOT, and 24 weeks post-EOT when all participants in the cohort completed the respective visits.	The Sponsor has decided to combine IA1 and IA2. As the study will be terminated earlier, the Sponsor also plans to merge IA3 with the final analysis.

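### Virological relapse (SAP exploratory endpoint 14) is a crude percentage with no follow-up rule although the study is ending early, so it would probably understate relapse over the planned follow-up

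*SAP*

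**What the plan says.** - **Summary.** SAP 4.5.1, endpoint 14: "The number and percentage of participants with virological relapse will be summarized during the study". It gives no time origin, at-risk set, censoring rule or interval estimate.
- **Definition.** The first limb needs a rise of at least 1 log10 "above nadir for at least 2 consecutive visits". The second limb, quantifiable HBV DNA at least 1 log10 above LLOQ after being below it, also needs two consecutive visits.
- **Denominator.** The section default is: "The analyses of the following exploratory efficacy endpoints will be conducted based on the FAS, unless otherwise specified".
- **Early termination.** SAP 4.10.1: "As the study will be terminated earlier, the Sponsor also plans to merge IA3 with the final analysis". For endpoints 9 and 11, SAP 4.4.1 changes the time points, and for two of its three analyses "the denominator used in the percentage calculation will exclude participants with uncertain NRTI discontinuation status due to early study termination".
- **Missing data.** SAP 4.1 has two general rules. One is "For efficacy response variables, the missing equals failure (MEF) approach will be used for the analysis". The other is "Missing data will not be imputed, and will be considered as missing data that will not be included in the data summary statistics". Neither mentions relapse.
- **Split.** SAP 4.1 also states that "Efficacy endpoints will be summarized by TDF/TD discontinued" and overall, for each cohort.

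This SAP is for STRIVE (V201). The supplied protocol is THRIVE (V202), which has the same relapse definition (Section 3) but reports no early stop.

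**The concern.** Relapse is an unfavourable event that takes time to occur and a second visit to confirm. When follow-up is shortened, a crude percentage loses events from the numerator and keeps the people in the denominator. Two groups are affected: participants cut off before they would have relapsed, and participants whose first high value is their last.

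For response endpoints, counting missing data as failure is conservative. For relapse, silence works the other way, because a participant with no further HBV DNA most naturally appears as a non-event. The relapse percentage will be read beside the sustained-suppression rates, which were adapted for early termination, so the two would not rest on the same footing.

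**Working it through.** The SAP gives no relapse rate, event count or length of lost follow-up, so there is no figure of its own to reproduce. Relapse risk and cut-off timing below are assumptions. The visit grids come from the SAP.

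**Step 1. Fixed cut-off.** Inputs:
- Visits after NRTI stop at F1 (SAP Table 12): F1, F2, F4, F6, F8, F10, F12, then every 4 weeks to F48.
- Assumed relapse risk R by F48, with constant hazard from F1: λ = −ln(1 − R)/47 and F(t) = 1 − exp(−λ(t − 1)).
- A rise is assumed to persist. It is confirmed if the next scheduled visit falls by the cut-off.

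If b is the last visit and a the one before it, then confirmed = F(a), unconfirmed = F(b) − F(a), and never observed = R − F(b).

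For R = 40%, λ = 0.5108/47 = 0.01087. At an F24 cut-off, F(20) = 1 − exp(−0.01087 × 19) = 18.7% and F(24) = 1 − exp(−0.01087 × 23) = 22.1%. Differences are taken before rounding.

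| Cut-off | Confirmed, % | Unconfirmed, points | Never observed, points |
|---|---|---|---|
| F24 | 18.7 | 3.5 | 17.9 |
| F36 | 28.6 | 3.0 | 8.4 |
| F48 (no early stop) | 37.3 | 2.7 | 0 |

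Lost follow-up is the larger part, and some confirmation loss occurs even with full follow-up. Participants who stay on NRTI have 12-week gaps after F24 (SAP Table 11). With the same assumed risk, their unconfirmed share is 9.5 points at an F36 cut-off and 8.4 at F48.

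**Step 2. Staggered cut-off.** NRTI is stopped at F1, the cut-off is uniform over weeks 16 to 56 and capped at F48, and 200,000 participants are simulated.

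| Assumed 48-week risk | Crude confirmed, % | Kaplan-Meier at F48, % | Confirmed with full follow-up, % | Crude shortfall, points | Single unconfirmed high at cut-off, points |
|---|---|---|---|---|---|
| 20% | 12.5 | 18.3 | 18.4 | 5.9 | 1.7 |
| 40% | 26.3 | 37.5 | 37.4 | 11.1 | 3.2 |
| 60% | 41.5 | 56.6 | 56.7 | 15.2 | 4.3 |

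The shortfall is the full-follow-up figure minus the crude figure. Kaplan-Meier recovers the full-follow-up figure to within 0.1 point. These figures are among NRTI stoppers. The FAS percentage also includes participants still on NRTI, so its shortfall would depend on how many stopped.

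**Step 3. How the missing-data rules could be read.** Take 3 confirmed relapses and 2 unresolved participants, in cohorts of the two initial sizes in SAP Section 5.

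| Reading | n = 15 | n = 10 |
|---|---|---|
| Unresolved stay in the denominator as non-relapsers | 3/15 = 20.0% | 3/10 = 30.0% |
| Unresolved excluded | 3/13 = 23.1% | 3/8 = 37.5% |
| Missing = failure, read as relapse | 5/15 = 33.3% | 5/10 = 50.0% |

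Under the last reading each unresolved participant adds 1/15 = 6.7 points or 1/10 = 10 points.

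**The case against.** **The direction is not written down.** A reader might infer that the plan counts cut-off participants as relapse-free. No section says so. The rule in SAP 4.3.1 that a missing value means not meeting the endpoint is confined to the primary endpoint. In SAP 4.1, failure could be read as relapse, which would overstate it, or missing values could be left out. This stands: understatement is the likely default, not a stated rule.

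**Relapse was not necessarily overlooked.** SAP 4.10.2 lists an update to the virological relapse summary in version 2.0, in the same row as the early-termination changes. What changed is not shown. It cannot be said that the old text was simply left in place, only that the current text has no follow-up rule.

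**Confirmation is the smaller mechanism.** This also stands (Steps 1 and 2). SAP 1.2.5 adds a prompt repeat after HBV DNA above 20,000 IU/mL and weekly visits after a fast rise, which could shorten the lag. However, the SAP does not say whether such visits confirm relapse. Under Appendix 2, a scheduled value takes precedence over an unscheduled one in the same window.

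**Weight.** The endpoint is exploratory and descriptive. Results are split by TDF/TD discontinuation, HBV DNA is plotted and listed for each participant, and retreatment is summarised separately. The all-participant analysis of endpoints 9 and 11 at the last follow-up visit would already show an unsuppressed last value. With small cohorts a reader could find unconfirmed rises. This lowers the priority, but it does not correct the percentage, and the split does not adjust for time off NRTI.

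**Restricting to NRTI stoppers would change the endpoint.** It would drop relapse on NRTI, which the definition covers. This stands, so the time-to-event estimate should be an addition.

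**Conclusion.** The gap is real and worth closing. The relapse summary has no follow-up rule in a study that is ending early. On the natural reading, confirmed relapses over the FAS, the percentage would probably understate relapse over the planned follow-up. Shortened follow-up accounts for most of this.

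The actual size cannot be computed. The shortfalls of about 6, 11 and 15 points rest on assumed risks, constant hazard, assumed cut-offs, NRTI stop at F1, persistent rises, no retreatment before confirmation and scheduled visits only.

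A reader might also infer that later-enrolled cohorts will look better. The documents give neither enrolment order nor cut-off dates, so that is not supported. Early termination is documented for STRIVE only.

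**What to change.** In SAP 4.5.1, endpoint 14:
- Keep the planned FAS count and percentage.
- Add, for participants who stopped TDF/TD, a Kaplan-Meier estimate of confirmed relapse from the date of NRTI stop, censored at the last HBV DNA, with numbers at risk.
- State how NRTI retreatment before confirmation enters the analysis (as an event, as censoring or as a separate category) and report how many participants it affects. SAP 1.2.5 recommends reinitiation after a single HBV DNA value above 100,000 IU/mL, so a second high visit may never occur.
- Report the number with an unconfirmed qualifying rise at the last available visit, and count them as relapse in a sensitivity analysis.
- State that missing-equals-failure does not mean no relapse for this endpoint, and choose one rule for unresolved participants.
- State whether unscheduled visits count as confirming.

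The cost is a few sentences of SAP text and one small table or curve, with no new data. The estimates will be imprecise because few participants are likely to stop NRTI.

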4.5.3. Exploratory Endpoints for Immunogenicity

The analyses of the immunogenicity exploratory endpoints will be conducted using the Immunogenicity Analysis Set and by cohort, unless otherwise specified.

Exploratory Endpoints	Analysis Methods
13. Incidence and titers of ADA (if applicable) to VIR-2218 (for cohorts with VIR-2218)	Not covered by this SAP, will be analyzed separately.

4.5.4. Exploratory Endpoints for Pharmacokinetics

The analysis of the PK exploratory endpoints will be conducted using the PK Analysis Set, unless otherwise specified.

Exploratory Endpoints	Analysis Methods
-----------------------	------------------

11. VIR-3434 PK parameters 12. VIR-2218 PK parameters (for cohorts with VIR-2218)	For a complete description of Pharmacokinetics Analysis, please see Section 4.8.1 .
--	---

4.6. Multiplicity Adjustment

Not applicable. This study is exploratory in nature, and no multiplicity adjustment will be made.

4.7. Safety Analyses

All safety analyses will be based on data from the TE Period for all participants in the Safety Analysis Set, unless otherwise specified. Data will be analyzed according to the treatment participants received in the Treatment Period. All safety data will be included in the individual participant listings.

The overall safety profile of the study intervention will be assessed in terms of the following safety and tolerability endpoints:

- TEAEs
- Clinical laboratory
- Laboratory Events of Clinical Interest (ECIs)

Only descriptive analysis of safety will be performed.

4.7.1. Extent of Exposure

Exposure summaries will be based on the Safety Analysis Set and presented by study intervention and by cohort and overall. Duration of exposure and the amount of dosage will be summarized.

Duration of exposure (weeks) of study intervention administration will be estimated as: (last dose date – first dose date + DoseFreq days) /7, regardless of dose interruption. DoseFreq will be 28 and 7 when the dosing frequency is every 4 weeks (Q4W) and once weekly (QW), respectively. DoseFreq for Cohort 3a will be either 56 or 84 when the VIR-3434 dosing is administered either every 8 weeks (Q8W) or every 12 weeks (Q12W), respectively. DoseFreq for TDF/TD that is administered daily will be 1 day. For an exposure duration involving more than one treatment, DoseFreq is the longest dosing frequency.

Duration of exposure will be summarized for all study interventions, including VIR-3434, VIR-2218, TDF/TD, and PEG-IFN α . Duration of exposure will be summarized as a continuous variable using descriptive statistics (n, mean, SD, median, Q1, Q3, min, max) by study intervention and cohort. The number and percentage of participants who received the full dose, dose interruption, dose reduction and study intervention discontinuation will be summarized as appropriate by study intervention and cohort.

The amount of dosage will be summarized as a continuous variable using descriptive statistics (n, mean, SD, median, Q1, Q3, min, max) by study intervention and cohort. All data related to exposure of study drug will be provided in a by-participant listing.

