1.2.3. Intervention Groups and Duration

There are 5 cohorts planned in this sub-study.

Table 3: Intervention Groups

Cohort	Study Drug	Dose	Route	Number of Doses	Frequency of Dosing
1a	VIR-3434	300 mg	SC	12	Every 4 weeks
	TDF	300 mg ^b	Oral	\geq 308 ^c	Every day
2a	VIR-3434	Up to 300 mg ^a	SC	12	Every 4 weeks
	TDF	300 mg ^b	Oral	\geq 308 ^c	Every day
3a	VIR-3434	300 mg	SC	4-6 ^d	Every 8-12 weeks ^d
	TDF	300 mg ^b	Oral	\geq 252 ^c	Every day
4a	VIR-3434	300 mg	SC	12	Every 4 weeks
	VIR-2218	200 mg	SC	12	Every 4 weeks
	TDF	300 mg ^b	Oral	\geq 308 ^c	Every day
5a	VIR-3434	300 mg	SC	13	Every 4 weeks
	VIR-2218	200 mg	SC	13	Every 4 weeks
	PEG-IFN α	180 mcg	SC	48	Every week
	TDF	300 mg ^b	Oral	\geq 336 ^c	Every day

^a The dose of VIR-3434 will be determined before participants are enrolled in the cohort.

^b Tenofovir disoproxil fumarate dose (TDF) will be 300 mg as approved by the FDA. Supply outside the United States may be Tenofovir disoproxil (TD) 245 mg.

^c The minimum number of doses received by participant. Participants will continue receiving additional doses of TDF until they qualify for NRTI discontinuation.

^d The dosing regimen will be finalized before participants are enrolled in the cohort.

The total duration in the study for participants will be up to 100 weeks in cohorts 1a, 2a, and Cohort 4a, 92-96 weeks for Cohort 3a, and 104 weeks for Cohort 5a. This includes a Screening Period (up to 56 days or 8 weeks), Treatment Period (44 weeks for cohorts 1a and 2a, 36 or

40 weeks for Cohort 3a, 44 weeks for Cohort 4a, and 48 weeks for Cohort 5a) and a Follow-Up Period (up to 48 weeks) for all cohorts.

Once participants complete the Treatment Period per their respective cohort, they will enter the Follow-Up Period. Participants will discontinue the NRTI at the F1 or F12 visit in the Follow-Up Period if they meet the criteria to discontinue NRTI ([Section 1.2.4](#)) based on the data available. Additional study visits are required for participants who discontinue NRTI in the Follow-Up Period as indicated in the SOA in the study protocol. Participants who discontinue NRTI at F1 visit will be required to return to the site for additional visits at F2, F6, F10, F28, F32, F40, and F44. Participants who discontinue NRTI at F12 visit will be required to return to the site for additional visits at F14, F18, F22, F28, F32, F40, and F44.

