1.2.4. NRTI Discontinuation

Participants will discontinue NRTI at F1 or at F12 Follow-Up visits based on the most recent data available if they meet all of the following criteria:

- HBsAg < LLOQ
- Suppressed HBV DNA (defined as < LLOQ)
- Undetectable HBeAg (based on quantitative HBeAg)
- ALT \leq 2 times the upper limit of normal (ULN).

Participants who meet the criteria to discontinue NRTI treatment will continue to be followed? per the Follow-Up Period SOA. Participants who meet NRTI discontinuation criteria but are not appropriate for NRTI discontinuation due to other reasons, based on the opinion of the Investigator, may continue on NRTI treatment following discussion with the Sponsor Medical Monitor to document the rationale for continuing NRTI.

Participants who do not qualify for NRTI discontinuation will continue taking the NRTI until the end of the Follow-Up Period. Once a participant has completed the study, long-term care should be determined by the Investigator or primary treating physician based on local clinical guidelines.

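### STRIVE SAP 4.7.1: combined exposure adds the longest dosing interval even when the last dose is a daily TDF tablet, overstating duration by up to 27 days (up to 55 or 83 in Cohort 3a)

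*SAP*

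**What the plan says.** SAP 4.7.1 computes duration of exposure in weeks as "last dose date – first dose date + DoseFreq days) /7, regardless of dose interruption" (the opening bracket stands just before these words). The interval depends on the drug:

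- Injections: "DoseFreq will be 28 and 7 when the dosing frequency is every 4 weeks (Q4W) and once weekly (QW), respectively".
- VIR-3434 in Cohort 3a: "DoseFreq for Cohort 3a will be either 56 or 84", for Q8W or Q12W dosing.
- Tablets: "DoseFreq for TDF/TD that is administered daily will be 1 day".
- Several drugs together: "For an exposure duration involving more than one treatment, DoseFreq is the longest dosing frequency".

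Other SAP sections fix when TDF stops. Table 3, note c (1.2.3): "Participants will continue receiving additional doses of TDF until they qualify for NRTI discontinuation". Section 1.2.4, for those who meet the criteria: "Participants will discontinue NRTI at F1 or at F12 Follow-Up visits based on the most recent data available". For the rest: "Participants who do not qualify for NRTI discontinuation will continue taking the NRTI until the end of the Follow-Up Period". The EOT date in 4.1 is set by the last dose of the injected drugs and leaves TDF out.

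Section 4.7.1 does not say which drug's last dose date enters a combined duration, and the SAP states no combined-exposure figure.

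**The concern.** Adding a dosing interval to the last dose date credits the time which that dose is taken to cover. This works for one drug. It also works for several drugs if the last dose given is the one with the longest interval. In STRIVE the planned order is the reverse: the injections stop at EOT and TDF goes on for between about 1 and 48 weeks. The rule then gives a tablet that covers one day a credit of 28, 56 or 84 days.

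At stake is the credibility of a reported safety summary. Some participants would show more weeks of exposure than they spent on study after Day 1. The excess would also differ between cohorts, being largest where injections are sparsest.

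**Working it through.** **Inputs (SAP).** Intervals are those of 4.7.1. From Table 3 and the visit days in Appendix 2, the last injection falls on Day 309 (Cohorts 1a, 2a, 4a), Day 337 (5a), Day 281 (3a, Q8W) or Day 253 (3a, Q12W). In Appendix 2, follow-up visit F1 is Day 8 ±2, F12 is Day 85 ±7 and F48 is Day 337 ±7. Taking the EOT date as follow-up Day 1, and the last tablet on the visit day, g is about 7 days (5 to 9) at F1, 84 (77 to 91) at F12 and 336 at F48.

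**Step 1: single-drug formula.** Table 3 gives at least 308 TDF doses for a 44-week Treatment Period: (308 − 1 + 1)/7 = 44.0 weeks, which agrees. Twelve Q4W injections: (309 − 1 + 28)/7 = 48.0. Cohort 3a Q8W: (281 − 1 + 56)/7 = 48.0. Cohort 3a Q12W: (253 − 1 + 84)/7 = 48.0. The single-drug rule is sound.

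**Step 2: combined duration.** Count days from the last injection. The SAP rule, with the last dose of any drug, ends exposure at g + L. If each drug is credited with its own interval and the latest end is taken, exposure ends at max(L, g + 1). For g ≥ 0:

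excess = g + L − max(L, g + 1) = min(g, L − 1).

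The ceilings are 28 − 1 = 27, 56 − 1 = 55 and 84 − 1 = 83 days.

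**Step 3: results at nominal visit days.**

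| Cohort | L (days) | TDF stops | SAP rule (weeks) | Own-interval benchmark (weeks) | Excess (days) |
|---|---|---|---|---|---|
| 1a, 2a, 4a | 28 | F1 | 49.0 | 48.0 | 7 |
| | | F12 | 60.0 | 56.1 | 27 |
| | | F48 | 96.0 | 92.1 | 27 |
| 5a | 28 | F1 | 53.0 | 52.0 | 7 |
| | | F12 | 64.0 | 60.1 | 27 |
| | | F48 | 100.0 | 96.1 | 27 |
| 3a, Q8W | 56 | F1 | 49.0 | 48.0 | 7 |
| | | F12 | 60.0 | 52.1 | 55 |
| | | F48 | 96.0 | 88.1 | 55 |
| 3a, Q12W | 84 | F1 | 49.0 | 48.0 | 7 |
| | | F12 | 60.0 | 48.1 | 83 |
| | | F48 | 96.0 | 84.1 | 83 |

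Across the visit windows, the F1 excess runs from 5 to 9 days. The F12 excess changes only for 3a Q12W, where it is 77 days at the early edge. If TDF ends on or before the day of the last injection, the excess is 0.

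Worst case written out (3a, Q12W, TDF to F48): the last tablet is on Day 253 + 336 = 589. SAP rule: (589 − 1 + 84)/7 = 672/7 = 96.0 weeks. Benchmark: the later of 253 − 1 + 84 = 336 days and 589 − 1 + 1 = 589 days, so 589/7 = 84.1 weeks. The excess is 672 − 589 = 83 days, or 83/589 = 14%.

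**Step 4: check against time on study.** From SAP 1.2.3, a 3a Q12W participant has 36 + 48 = 84 weeks after Day 1, against 96.0 weeks of reported exposure. Cohorts 1a, 2a and 4a have 44 + 48 = 92 weeks, also against 96.0. With TDF to F48, these cohorts and both 3a schedules all report 96.0 weeks, although the benchmarks are 92.1, 88.1 and 84.1.

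**The case against.** The best defence is that the SAP never says which last dose date a combined duration uses. Its EOT date excludes TDF, and 4.7 analyses safety data by treatment received in the Treatment Period. Anchored at EOT, the excess is zero. The gap in wording is real, but no passage applies the EOT anchor to exposure, and 4.7.1 lists TDF/TD among the study interventions with its own interval. That anchor would also make combined exposure shorter than one of its parts: 48.0 weeks in Cohort 1a, where TDF alone to F48 gives (645 − 1 + 1)/7 = 92.1.

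Two further objections limit the point without removing it. Cohort 3a's schedule is left open in Table 3 (8- to 12-weekly), so 83 days applies only if Q12W is used. SAP 4.10.1 also records early termination, so fewer participants reach F48. However, the ceiling is reached once g is 27, 55 or 83 days, so F48 is not needed.

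A reader might infer that everyone whose last dose is a tablet gains 27 to 83 days. That does not follow: those figures are maxima, and stopping TDF at F1 gives about 7 days in every cohort. A reader might also infer that safety rates are biased through an inflated denominator. The SAP does not support this. TEAEs, laboratory abnormalities and ECIs are counts and percentages of participants, compliance is dosage taken over dosage planned, and the TE Period has its own drug-specific rules.

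**Conclusion.** The point holds, as a minor one. On the natural reading of the last dose date, the combined-exposure rule overstates duration in STRIVE by min(g, L − 1) days. The size depends on when TDF stops:

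- **About F12 or later:** up to 27 days in the Q4W cohorts, and up to 55 (Q8W) or 83 (Q12W) days in Cohort 3a.
- **At F1:** about 7 days.
- **With the last injection:** 0.

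The SAP does not give the shares of participants stopping at each point, so no mean excess can be stated.

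Only the descriptive summary of combined exposure is touched. Per-drug exposure is correct, and no efficacy result, compliance rate, TEAE table or TE Period depends on the rule. No formal comparison between cohorts is planned, so the unequal excess affects only how the descriptive figures read side by side.

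The point concerns STRIVE, which the SAP covers. The protocol supplied is THRIVE, which has no Cohort 3a and ends TDF with the last VIR-3434 or VIR-2218 dose (4.3.3). The same rule would give no excess there.

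**What to change.** Replace the sentence on multi-treatment durations in SAP 4.7.1 with a definition along these lines: for each drug, add that drug's own DoseFreq to its last dose date; take the latest of these dates; subtract the first dose date of any drug; divide by 7. This also settles which last dose date is meant. It agrees with the single-drug formula and leaves the result unchanged when TDF ends no later than the last injection. The cost is one sentence in the SAP and the matching line in the exposure program. No new data are needed.
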